**Table 7.1 Ponatinib: Dose Modifications for Drug Adverse Reactions**

Toxicity	Modification
Nonhematologic Toxicity	
General (Any CTCAE v4.0 nonhematologic toxicity not otherwise specified below)	
Grade 1 or transient Grade 2	No intervention
AST/ALT Elevations	
Grade 1 or transient Grade 2	No intervention
Grade 2 lasting $\geq$ 7 days with optimal care AND total bilirubin $<$ 2 x ULN	Hold ponatinib Resume at 30 mg after recovery to $\leq$ grade 1  Recurrence at 30 mg: Hold ponatinib Resume at 15 mg after recovery to $\leq$ grade 1  Recurrence at 15 mg Discontinue ponatinib
Grade 3 or 4 AND total bilirubin $<$ 2 x ULN	Hold ponatinib Resume at 30 mg after recovery to $\leq$ grade 1  Recurrence at 30 mg Hold ponatinib Resume at 15 mg after recovery to $\leq$ grade 1  Recurrence at 15 mg Discontinue ponatinib
Grade $\geq$ 2 AND total bilirubin $\geq$ 2 x ULN (In the absence of liver metastases)	Discontinue ponatinib
Pancreatitis	
Grade 2 (enzyme elevation or radiologic findings only)	See amylase/lipase section below
Grade 3 (severe pain, vomiting, medical intervention indicated [eg, analgesia, nutritional support])	Hold ponatinib Perform ultrasound or abdominal CT scan with contrast If imaging is positive, continue holding ponatinib and repeat according to clinical care. If imaging is negative, or after resolution by imaging, resume at 15 mg after recovery to $\leq$ grade 1  Recurrence at 15 mg: Repeat above Consider discontinuing ponatinib
Grade 4	Hold ponatinib Consult sponsor
Amylase/Lipase	
Grade $\leq$ 2	No intervention; monitor closely

Toxicity	Modification
Grade 3 with no radiologic findings	Hold ponatinib Resume at 30 mg after recovery to $\leq$ grade 1  Recurrence at 30 mg: Hold ponatinib Resume at 15 mg after recovery to $\leq$ grade 1  Recurrence at 15 mg: Discontinue ponatinib
Grade 3 with radiologic findings or Grade 4	Hold ponatinib Repeat imaging according to clinical care After resolution by imaging, resume at 15 mg after recovery to $\leq$ grade 1  Recurrence at 15 mg: Discontinue ponatinib
LV dysfunction/CHF	
Grade 2 or 3	Hold ponatinib Resume at 30 mg after recovery to $\leq$ grade 1  Recurrence at 30 mg: Hold ponatinib Resume at 15 mg after recovery to $\leq$ grade 1  Recurrence at 15 mg: Discontinue ponatinib
Grade 4	Discontinue ponatinib
Skin rash	
Grade 2 persistent despite optimal symptomatic therapy	Hold ponatinib Resume at 30 mg after recovery to $\leq$ grade 1  Recurrence at 30 mg: Hold ponatinib Resume at 15 mg after recovery to $\leq$ grade 1  Recurrence at 15 mg: Discontinue ponatinib
Grade 3 persistent despite optimal symptomatic therapy	Hold ponatinib Resume at 30 mg after recovery to $\leq$ grade 1  Recurrence at 30 mg: Hold ponatinib Resume at 15 mg after recovery to $\leq$ grade 1  Recurrence at 15 mg: Discontinue ponatinib

Toxicity	Modification
Hematologic Toxicity	
Drug-Related ANC/platelets	
Grade 1 or 2	No dose adjustment
Grade 3 or 4	Hold ponatinib Resume at 30 mg after recovery to $\leq$ grade 1  Recurrence at 30 mg: Hold ponatinib Resume at 15 mg after recovery to $\leq$ grade 1  Recurrence at 15 mg: Discontinue ponatinib

Definitions: ANC = absolute neutrophil count; CHF = congestive heart failure; CT = computed tomography; LV = left ventricular.

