##### **3.1.1 Signed informed consent.**

- 3.1.2 Age  $\geq$  18 years.
- 3.1.3 Histologically or cytologically confirmed advanced (stage IIIB or IV) NSCLC.
- 3.1.4 Molecular confirmation of a RET translocation is required to begin protocol therapy. Methods of acceptable molecular confirmation include RET FISH and next-generation sequencing performed in a CLIA certified lab.
- 3.1.5 At least one measurable lesion as defined by RECIST v1.1 criteria. Previously irradiated lesions are not measurable unless the lesion has demonstrated clear progression after radiation. See [Section 9.0](#) for the evaluation of measurable disease.
- 3.1.6 Eligible participants must have received at least one line of prior therapy. Note: Patients will be eligible for participation despite prior treatment with known RET TKIs (e.g. vandetanib, sorafenib, XL-184).
- 3.1.7 Performance status score of 0-2 according to the Eastern Cooperative Group (ECOG) scale.
- 3.1.8 Estimated life expectancy  $\geq$  12 weeks.
- 3.1.9 Able to swallow and retain orally administered medication. Does not have any clinically significant gastrointestinal abnormalities, such as malabsorption syndrome or major resection of the stomach or small bowel that may alter absorption of the medication.
- 3.1.10 Adequate bone marrow function as defined by the following criteria:
  - Absolute neutrophil count (ANC)  $\geq 1.5 \times 10^9/L$
  - Hemoglobin  $\geq 9 \text{ g/dL}$
  - Platelets  $\geq 100 \times 10^9/L$
- 3.1.11 Adequate hepatic function as defined by the following criteria:
  - Total serum bilirubin  $\leq 1.5 \times$  upper limit of normal (ULN), unless due to Gilbert's syndrome.
  - Alanine aminotransferase (ALT)  $\leq 2.5 \times$  ULN
  - Aspartate aminotransferase (AST)  $\leq 2.5 \times$  ULN
- 3.1.12 Adequate renal function as defined by the following criteria:
  - Serum creatinine  $< 1.5 \times$  ULN
- 3.1.13 Adequate pancreatic function as defined by the following criterion:
  - Serum lipase and amylase  $\leq 1.5 \times$  ULN

- 3.1.14 Women of childbearing potential must have a negative pregnancy test.
- 3.1.15 Female and male patients who are of childbearing potential must agree to use an effective form of contraception with their sexual partners from enrollment through 30 days after the end of treatment.
- 3.1.16 Willingness and ability to comply with scheduled visits and study procedures.

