### **6.11 Required Concomitant Therapy**

Ponatinib has been associated with an increased risk for arterial thrombotic events, such as myocardial infarction, peripheral vascular disease and cerebrovascular accident.

Thromboprophylaxis is required for all participants receiving ponatinib. It is recommended that participants receive daily aspirin (81 or 325 mg). Note: This does not apply to participants who are already receiving therapeutic anticoagulation (e.g. low molecular weight heparin), provided that these participants meet the eligibility criteria outlined in [Sections 3.1 and 3.2](#). It is recommended that if the platelet count falls below 50,000/mm^3, thromboprophylaxis be held to minimize the risk of bleeding. It should then be resumed when platelet counts are equal to or above this level.

All patients should also be treated with a statin to reduce the risk of cardiovascular events. We recommend atorvastatin (Lipitor) administered at a minimum of 10 mg/day, but other statins and doses may be substituted if appropriate. The specific regimen should correspond with moderate-intensity or high-intensity statin therapy as defined by the recent AHA/ACC guidelines (Stone et al, Circulation 2013,

<http://circ.ahajournals.org/content/suppl/2013/11/07/01.cir.0000437738.63853.7a.DC1.html>).

High-intensity therapy should be considered in patients in high risk categories, such as those with a history of cardiovascular disease, diabetes, or LDL cholesterol greater than 190 mg/dL, but patient age and risk of side effects due to statin therapy (myopathy, elevated CPK, elevated liver enzymes) should be taken into consideration. Measurement of cholesterol and dose adjustment to meet a cholesterol target is not necessary but could be considered to ensure compliance or per physician or patient preference.

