### **7.3 Dose Delay and/or Reduction for Adverse Events (AEs) Attributable to the Study Drug**

[Table 7.1](#) describes suggested guidelines for dose modification due to study-drug-related toxicity, graded according to NCI CTCAE 4.0. However, for an individual participant, dose interruptions, reductions and treatment discontinuation should also be based on the clinical circumstance and investigators should use clinical judgment in deciding whether a dose reduction, delay or discontinuation is appropriate for any given clinical circumstance. In general, when the observed toxicity has resolved to  $\leq$  grade 1, the investigator may resume full dosing if clinically indicated.

No dose reduction below 15 mg once daily is permitted for ponatinib. If the participant cannot tolerate a minimum dose of 15 mg per day of ponatinib, despite any allowed interruptions, the participant must be discontinued from study treatment. Doses may be interrupted for study-drug related toxicities for up to 28 days. If a non-hematologic study-drug related toxicity does not resolve to Grade 1 or less after dose interruption for more than 28 days, the participant must be discontinued from study treatment. If a hematologic study-drug related toxicity does not resolve to Grade 1 or less after dose interruption for more than 28 days, the Principal Investigator/Sponsor must be contacted. Additionally, the Principal Investigator/Sponsor must be contacted if any adverse event deemed unrelated to treatment requires dose interruption for more than 28 days. Lastly, for each participant, once a dose reduction has occurred, the dose level may not be re-escalated during subsequent treatment cycles of ponatinib.

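### Table 7.1 assigns two opposite actions to a transient grade 2 AST/ALT rise with total bilirubin at or above 2 x ULN and no liver metastases, and no action to three related combinations

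*Combined protocol and SAP*

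**What the plan says.** Table 7.1 has four rows for AST/ALT elevations.

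- **First row.** The trigger is "Grade 1 or transient Grade 2" and the action is no intervention. Neither bilirubin nor liver metastases is mentioned.
- **Second row.** Grade 2 lasting at least "7 days with optimal care AND total bilirubin" below 2 x ULN: hold, then resume or reduce.
- **Third row.** "Grade 3 or 4 AND total bilirubin" below 2 x ULN: the same hold sequence.
- **Fourth row.** Grade 2 or higher with total bilirubin at or above "2 x ULN (In the absence of liver metastases"): discontinue. Duration is not mentioned.

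Section 7.3 says that the table "describes suggested guidelines for dose modification due to study-drug-related toxicity", and that "investigators should use clinical judgment in deciding whether a dose reduction, delay or discontinuation is appropriate". Section 7.5.7 (Hepatotoxicity) names transaminase elevation and hyperbilirubinemia as observed effects and sends the reader back to Table 7.1. At entry, criterion 3.1.11 caps total bilirubin at 1.5 times the "upper limit of normal (ULN), unless due to Gilbert's syndrome".

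**The concern.** A dose-modification table works only if each clinical picture leads to one instruction. Here the two hold rows carry a bilirubin condition but the first row does not, and the stop row carries no duration condition. The first and last rows therefore overlap, and their actions are the two extremes available in the block.

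Within the AST/ALT block, the fourth row is the only one that calls for discontinuation at first occurrence, so the table itself treats the combined enzyme and bilirubin rise as its most serious case. For one form of that case, another row asks for no action. Section 13.2 expects three hospitals to enrol, and two of them could treat the same participant in opposite ways while each followed the table.

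**Working it through.** The plan states no figure on this point, so there is none to reproduce. The check is one of logic.

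**Inputs (Table 7.1, AST/ALT rows)**

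| Row | AST/ALT grade | Duration | Total bilirubin | Liver metastases | Action |
|---|---|---|---|---|---|
| 1 | 1, or transient 2 | transient, for grade 2 | no condition | no condition | none |
| 2 | 2 | at least 7 days | < 2 x ULN | no condition | hold |
| 3 | 3 or 4 | no condition | < 2 x ULN | no condition | hold |
| 4 | 2 or higher | no condition | ≥ 2 x ULN | absent | stop |

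**Assumption.** The protocol does not define transient. I take it as the complement of row 2, that is, not lasting 7 days or more.

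**Enumeration.** Grade 1, transient grade 2, grade 2 lasting at least 7 days, grade 3 and grade 4 make 5 levels. With two bilirubin levels and liver metastases absent or present, there are 5 × 2 × 2 = 20 combinations.

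| AST/ALT | Bilirubin < 2 x ULN (either metastasis status) | Bilirubin ≥ 2 x ULN, no liver metastases | Bilirubin ≥ 2 x ULN, liver metastases |
|---|---|---|---|
| Grade 1 | row 1, none | row 1, none | row 1, none |
| Grade 2, transient | row 1, none | **rows 1 and 4, none and stop** | row 1, none |
| Grade 2, at least 7 days | row 2, hold | row 4, stop | **no row** |
| Grade 3 | row 3, hold | row 4, stop | **no row** |
| Grade 4 | row 3, hold | row 4, stop | **no row** |

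**Count**

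- The first bilirubin column holds 5 × 2 = 10 combinations, each with one action.
- The second holds 5: four with one action and one with two opposite actions.
- The third holds 5: two with one action and three with none.
- In total, 10 + 4 + 2 = 16 have exactly one action, 1 has two, and 3 have none; 16 + 1 + 3 = 20.

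**Does the conflict depend on the assumption?** No. Row 4 ignores duration, so any grade 2 rise that counts as transient, however defined, also meets row 4 when bilirubin is at or above 2 x ULN and there are no liver metastases. A narrower meaning of transient would only add uncovered combinations between rows 1 and 2.

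**Is there a tie-break elsewhere?**

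- Section 7.2 says that modifications are made as the following sections indicate; it gives no order.
- Section 7.3 gives the guideline status, the judgment clause and the 28-day interruption limit; it gives no order of rows.
- Section 7.5.7 points back to the table.
- The general non-hematologic block at the head of Table 7.1 covers only toxicities not specified further down and, in the text available, lists only grade 1 or transient grade 2. It neither settles the overlap nor fills the three empty combinations.

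**The case against.** The strongest answer is Section 7.3. The table offers suggested guidelines for drug-related toxicity, and the investigator is told to use judgment about reduction, delay or discontinuation. On that footing no site is compelled either to do nothing or to stop. One can add that the row naming both enzymes and bilirubin is the more specific, so an ordinary reader would let it prevail.

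The first part stands and limits the consequence: this is a drafting conflict in a guideline, not a binding instruction to do harm. It does not remove the conflict, because permission to depart from a rule does not say which of two opposite rules is the default. The specificity reading is reasonable, but the protocol does not state it. It also does nothing for the three combinations with no row.

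A reader might infer more than the text supports in four ways.

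- **Gilbert's syndrome as a second contradiction.** Criterion 3.1.11 waives the bilirubin limit for Gilbert's syndrome without another ceiling, and the stop row excepts only liver metastases. Someone admitted at or above 2 x ULN would meet the bilirubin half of that row from the start. But an entry limit and an on-treatment rule need not match, and the row still requires a drug-related enzyme rise of grade 2 or higher. Nobody is stopped for entry bilirubin alone. This is an omission and a secondary point.
- **The required statin as a cause.** Section 6.11 says that the "risk of side effects due to statin therapy (myopathy, elevated CPK, elevated liver enzymes) should be taken into consideration". A rise attributed to the statin is not study-drug-related and so falls outside Table 7.1 as Section 7.3 describes it.
- **A frequency from Table 2.2.** ALT increase in 23/449 (5.1%) would give 1 − (1 − 23/449)^20 = 65% for at least one case in 20. That counts every grade, has no bilirubin condition, and comes from leukemia patients at 45 mg, whereas this trial starts at 30 mg and Section 2.3 says ALT/AST elevation appeared to correlate with dose. Removing the 8 grade 3 or 4 cases leaves 15/449 (3.3%), and 1 − (1 − 15/449)^20 = 49%, which still includes grade 1 and ignores bilirubin. Neither figure measures the event in question.
- **A loss of 5 points of ORR per participant stopped.** One of 20 is 5 points, but only if stopping prevents a response that would otherwise occur. Section 1.4 counts a response at any point post treatment, and Section 5.7 continues tumor assessments after a stop without progression until another anti-cancer therapy begins.

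**Conclusion.** The AST/ALT rows of Table 7.1 are inconsistent as written. One of 20 combinations carries opposite actions, and three of 20 carry none. The counts rest on reading transient as shorter than 7 days; the conflict itself does not.

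The point concerns participant safety and uniform conduct across sites. It does not show a bias in the primary endpoint or a need to change the sample size. The documents give no frequency for bilirubin at or above 2 x ULN together with an enzyme rise, nor for Gilbert's syndrome, so the number of participants affected cannot be estimated. It is likely to be small. The guideline status of the table reduces the weight of the point further, but the correction is cheap and the two conflicting instructions lie at opposite extremes.

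**What to change.** Reword the AST/ALT rows of Table 7.1 so that every combination of grade, duration, total bilirubin and liver metastases leads to exactly one action. That means three things:

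- resolve the overlap between the first and last rows;
- supply an entry for bilirubin at or above 2 x ULN with liver metastases when AST/ALT is grade 2 for at least 7 days, grade 3 or grade 4;
- define transient.

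In the same edit, check the stop row against the Gilbert's exception in 3.1.11 and state how those participants are to be read. Which action applies in each case is for the sponsor to set.

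The cost is wording in a few table rows and IRB approval of the amendment under Section 12.1. No new assessment is needed: Section 5.1 already puts AST, ALT and total bilirubin with its fractions in the serum chemistry panel, and imaging of the abdomen in the screening assessment.

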### **7.5.4 Pancreatitis and Amylase or Lipase Elevations**

Pancreatitis (symptomatic abdominal pain associated with pancreatic enzyme elevation) and/or elevations in lipase and amylase are known AEs associated with ponatinib. Pancreatitis was reported in 7% of patients in the phase 2 study of ponatinib and 12% in the phase 1 dose-escalation study. Most cases of pancreatitis or elevated pancreatic enzymes occur within the first month of treatment with ponatinib. The events are generally uncomplicated and reversible and can be managed with a brief interruption of treatment and standard medical therapies. Almost all patients are able to continue on with ponatinib treatment at the same or a reduced dose once the event has improved to grade 1 or resolved.

Patients with low-grade (1 or 2) elevation in amylase can be continued without dose reduction but should be monitored closely with serial enzyme level determinations.

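### Table 7.1 leaves stopping optional when grade 3 pancreatitis recurs at 15 mg, while every other row with that step, including the two enzyme rows, says to discontinue

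*Combined protocol and SAP*

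**What the plan says.** The grade 3 pancreatitis row of Table 7.1 covers a symptomatic event needing medical intervention. It calls for a hold and imaging. If imaging is positive the hold goes on: "If imaging is positive, continue holding ponatinib and repeat according to clinical care". Otherwise, "If imaging is negative, or after resolution by imaging, resume at 15 mg", once the event has recovered to grade 1 or less. On recurrence at 15 mg the row reads "Repeat above Consider discontinuing ponatinib".

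The amylase/lipase block has three lines. Grade 2 or lower needs monitoring only. The line headed "Grade 3 with no radiologic findings" restarts at 30 mg, steps to 15 mg on recurrence, and discontinues on recurrence at 15 mg. The line for grade 3 with radiologic findings, or grade 4, restarts at 15 mg after imaging resolves and discontinues on recurrence at 15 mg.

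Within the pancreatitis block, only grade 2 (enzyme or imaging findings alone) is referred to the amylase/lipase block.

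Section 7.3 says that the table "describes suggested guidelines for dose modification due to study-drug-related toxicity", to be applied with clinical judgment. It also sets firm limits. No dose below 15 mg is allowed. If 15 mg cannot be tolerated, "despite any allowed interruptions, the participant must be discontinued from study treatment". A non-hematologic drug-related toxicity that has not resolved to grade 1 or less after an interruption of more than 28 days also requires discontinuation.

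Section 7.5.4 treats enzyme elevation as part of pancreatitis, "Pancreatitis (symptomatic abdominal pain associated with pancreatic enzyme elevation", but names no enzyme grade.

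**The concern.** As printed, the stopping instruction is weaker for the symptomatic event than for the laboratory finding at the same dose, and no reason is given. Pancreatic events were the phase 1 dose-limiting toxicity (Section 2.1), and Section 13.2 expects enrollment from three hospitals. Two sites could each follow the document and reach different decisions on permanent discontinuation of comparable participants. In one combination of findings they could also restart at different doses. Time on treatment and the recorded reason for stopping would then depend partly on which line was read. With 20 participants, one or two such cases would be visible in the safety and tolerability summary.

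**Working it through.** No sample-size, power or error-rate figure underlies this point. The check is a comparison of text, followed by a short calculation of how often the situation might arise.

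**Step 1: recurrence at 15 mg.** Nine rows of Table 7.1 contain this step.

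| Toxicity | Rows | Instruction on recurrence at 15 mg |
|---|---|---|
| AST/ALT (persistent grade 2; grade 3 or 4) | 2 | Discontinue |
| Pancreatitis, grade 3 | 1 | Repeat the cycle; consider discontinuing |
| Amylase/lipase (grade 3 without findings; grade 3 with findings or grade 4) | 2 | Discontinue |
| LV dysfunction/CHF, grade 2 or 3 | 1 | Discontinue |
| Skin rash (grade 2; grade 3) | 2 | Discontinue |
| ANC/platelets, grade 3 or 4 | 1 | Discontinue |

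Eight of nine rows (2 + 2 + 1 + 2 + 1 = 8) say discontinue. The cycle to be repeated in the pancreatitis row is hold, image, resume at 15 mg. The row therefore permits a further restart and does not say how many times. This inconsistency does not depend on any participant meeting two rows at once.

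**Step 2: Section 7.3.** Two readings are open. Recurrence at 15 mg may itself show that 15 mg is not tolerated, in which case discontinuation is compulsory. Or the repeated hold may be an allowed interruption, in which case intolerance has not yet been shown. The text does not choose.

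**Step 3: restart dose.** Take a participant with grade 3 pancreatitis and vary the enzyme grade and imaging.

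| Enzymes and imaging | Pancreatitis row | Amylase/lipase line | Result |
|---|---|---|---|
| Grade 2 or lower | 15 mg | Monitor only | No competing restart dose |
| Grade 3, imaging negative | 15 mg | 30 mg | Differ |
| Grade 3, imaging positive | 15 mg after resolution | 15 mg after resolution | Agree |
| Grade 4 | 15 mg | 15 mg | Agree |

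The doses differ in one combination only, and only if the amylase/lipase lines are read as covering symptomatic participants. The table neither says nor excludes this.

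**Step 4: length of hold.** Both blocks hold until recovery to grade 1 or less, and until imaging resolves where there are findings. Neither states a time limit. The 28-day limit in Section 7.3 is general and can be applied on top of both.

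**Step 5: frequency.** Table 2.2 gives 21 of 449 participants with treatment-related grade 3-4 pancreatitis. These had CML or Ph+ ALL and were treated at 45 mg.

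- Rate: 21/449 = 0.0468, the 4.7% stated.
- Expected in 20 participants: 20 × 0.0468 = 0.94, about 0.9.
- Chance of at least one: 1 − (1 − 0.0468)^20 = 0.616, about 62%.

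These are ceilings for the situations at issue. The 21 include grade 4 cases, which have a separate line in Table 7.1. If a fraction r of the 0.94 went on to recur at 15 mg, the expected number would be 0.94 × r, anywhere from 0 to 0.94. The documents give no value for r, and none for the share with grade 3 enzymes and negative imaging.

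**The case against.** The best defense is the table's own routing. Only grade 2 pancreatitis is sent to the enzyme block, while grade 3 has a complete instruction of its own. The natural inference is that symptomatic grade 3 disease follows its own row and the enzyme lines are for enzyme or imaging findings alone. On that reading there is no overlap, and 15 mg and 30 mg are instructions for different events. This is plausible and may be what was meant, but the table does not say it. It also leaves the recurrence difference in Step 1 untouched.

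Second, Section 7.3 calls the table suggested guidance and invites clinical judgment, so some variation between sites is by design. That lowers the severity. It does not tell a site which printed instruction is the guidance, and the Section 7.3 stopping sentences are themselves worded as compulsory.

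Third, Section 7.5.4 describes these events as generally reversible, with almost all patients able to continue, so the softer wording may be deliberate. But that passage covers pancreatitis and enzyme elevations together, so it does not explain why the two are treated differently on recurrence.

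A reader might infer more than the documents support:

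- That every participant with grade 3 pancreatitis meets both blocks. The definition in Section 7.5.4 requires no enzyme grade.
- That the two blocks disagree on length of hold. They do not. At most a pointer to the 28-day limit is missing, and no other row of the table repeats that limit either.
- That the instructions are opposites. Considering discontinuation and discontinuing differ in strength.
- That the all-grade pancreatitis rates of 7% and 12%, or the 7.8% rate of grade 3-4 lipase increase, measure the problem (20 × 0.07 = 1.4; 20 × 0.12 = 2.4; 20 × 0.078 = 1.6). They count broader events than the ones in conflict.

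**Conclusion.** The inconsistency on recurrence at 15 mg is established from the text. Grade 3 pancreatitis is the sole exception among nine rows, and its fit with the compulsory sentence in Section 7.3 is unclear. The restart-dose ambiguity is real but confined to grade 3 enzymes with negative imaging, and the routing of grade 2 points to a likely, unstated answer. There is no conflict on length of hold.

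The expected number of grade 3-4 pancreatitis cases is about 0.9 of 20, assuming that the rate seen at 45 mg in leukemia patients applies here. The rate at 30 mg in lung cancer may differ. The conflicting situations are subsets of unknown size.

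The rule of at least 4 responses in 20 (Section 13.1) and its stated power and type 1 error do not depend on this point. It should be corrected, but it falls short of a defect that must be fixed before the trial can proceed.

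**What to change.** Reconcile the grade 3 pancreatitis row, the two grade 3/4 amylase/lipase lines and Section 7.3 on what happens at recurrence on 15 mg. Say whether a repeated hold is an allowed interruption under Section 7.3. State in Table 7.1 which row governs when a participant meets both, so that grade 3 pancreatitis with grade 3 enzymes and negative imaging has a single restart instruction. Add a cross-reference from both blocks to the 28-day limit. If the difference on recurrence is intended, a sentence giving the reason would settle the matter. The choice of dose and stopping rule belongs to the sponsor, and no view on it is offered here.

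The cost is a wording change in the next amendment, with the usual IRB approval (Section 12.1). No participants, visits or procedures are added.
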